**Statistical Analysis Plan (SAP):**

Descriptive statistics will be used to define baseline demographic characteristics of patients. Patients' data and clinical parameters will be given as means with standard deviation (SD), for normally distributed variables; and as median with range or interquartile range (IQR) in parenthesis as indicated, for non-normally distributed variables. Differences between the continuous variables during the control and the intervention period will be analyzed by t-test or the Mann-Whitney U test for normally or non-normally distributed variables respectively. Paired, Two-tailed tests with a significance level of 5% will be used in all analyses. All calculations will be performed using IBM statistics SPSS v25.

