#### **Study design:**

This is a 4 week open-label, non-blinded, non randomized study in patients with fecal incontinence.

The study will consist of two periods of two weeks:

- First two weeks - control period: Patients will be asked to continue his / her normal life and to answer to validated questionnaires of fecal incontinence, quality of life and to fill a stool diary.
  - The first week will be considered as the baseline period
  - The second week as the control period.

- Second two weeks - treatment period: Patients will be provided with the device, and ask to answer to the same questionnaires, stool diary and an additional usability questionnaire.

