### **Number of patients:**

In this study each patient will be his own control before and after the intervention. We expected minimal change (if any) during the control period. We calculated that 20 patients in each group are required to have a 80% chance of detecting, (with a significant 5% level), an increase in 5 points in the quality of life questionnaire from 20% in the control period to 60% in the treatment period.

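### The SAP names the Mann-Whitney U test for non-normal before/after comparisons but requires every test to be paired; both instructions cannot be followed

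*Combined protocol and SAP*

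**What the plan says.** The Statistical Analysis Plan section deals with "Differences between the continuous variables during the control and the intervention period" and states that these "will be analyzed by t-test or the Mann-Whitney U test for normally or non-normally distributed variables respectively". The sentence that follows sets a rule for the whole plan: "Paired, Two-tailed tests with a significance level of 5% will be used in all analyses".

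Two other sections establish the data structure. Under Study design: "This is a 4 week open-label, non-blinded, non randomized study in patients with fecal incontinence". In the treatment period the same patients are again "ask to answer to the same questionnaires, stool diary and an additional usability questionnaire". Under Number of patients: "In this study each patient will be his own control before and after the intervention". Study procedures has each patient complete the quality-of-life and Wexner questionnaires on days 0, 7, 14, 21 and 28.

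No section names a paired rank test.

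**The concern.** The t-test has a paired version, so the normal branch can be carried out as the second sentence requires. The Mann-Whitney U test cannot, because it ranks two independent samples against each other and ignores which values come from the same patient. For a non-normal variable the analyst must break one of the two sentences, and the p-value depends on which.

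The variables at stake are the quality-of-life scores, the Wexner total and components, and the diary counts, when analysed as continuous. With about 20 patients, bounded scores and episode counts, the non-normal branch may well be used. The responder outcomes are not affected. Nor are usability, satisfaction and willingness to continue, which are collected only on day 28 and have no control-period value to compare.

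If the named test is run, repeated values on the same patient usually correlate positively, so it would use too large a variance for the change. A real change could then be missed.

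**Working it through.** **1. The plan's own figure.** Number of patients states "We calculated that 20 patients in each group are required to have a 80% chance of detecting" "an increase in 5 points in the quality of life questionnaire from 20% in the control period to 60% in the treatment period". The unpooled formula for two independent proportions, two-sided 5%, 80% power, gives

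n = (1.960 + 0.842)² × (0.2×0.8 + 0.6×0.4) / 0.4² = 7.849 × 0.40 / 0.16 = 19.6, rounded up to 20.

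The stated 20 is reproduced. It rests on responder proportions, so the choice of rank test does not affect it.

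**2. The sentences side by side.**

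| Branch | Test named | Paired form exists? | Compatible with the paired rule? |
|---|---|---|---|
| Normal | t-test | Yes | Yes |
| Non-normal | Mann-Whitney U | No | No |

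The contradiction needs no calculation. The rest concerns what follows if the named test is run.

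**3. Direction of the error.** Take equal variances σ² in both periods and within-patient correlation ρ. The mean change has variance 2σ²(1−ρ)/n, whereas an independent-samples test assumes 2σ²/n. Under no effect its standardised statistic has variance of about 1−ρ, so the true error rate is roughly 2 × [1 − Φ(1.96/√(1−ρ))]. At ρ = 0.3 this is 2 × [1 − Φ(2.34)] = 1.9%; at ρ = 0.5 it is 2 × [1 − Φ(2.77)] = 0.6%. This is a large-sample guide; the simulations below use 20 pairs.

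**4. Simulation set-up.** From the plan: 20 patients, two-sided 5%. Assumed, because the documents give no SD, correlation, distribution or continuous effect: correlations of 0 to 0.8 and four data models.

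- Normal, with a mean change of 0.660 SDs of the differences (80% paired-t power).
- Log-normal (log-scale SD 1, correlation on the log scale), with a proportional change.
- The same log-normal, with an additive shift.
- Negative binomial counts (mean 5, size 1.5, Gaussian copula), with ties and zero differences.

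In the three non-normal models the effect was set so that signed-rank power was about 78% (77 to 79% achieved); in the normal model it was also about 78%. All tests were asymptotic, with tie correction.

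**5. Results for Mann-Whitney.**

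| Assumed correlation | 0 | 0.3 | 0.5 | 0.7 | 0.8 |
|---|---|---|---|---|---|
| Type I error, all four models (%) | about 5 | 2.1–2.4 | 0.7–0.9 | 0.1–0.2 | below 0.05 |
| Power, normal (%) | 80 | 67 | 51 | 26 | 11 |
| Power, tied skewed counts (%) | 76 | 62 | 49 | 24 | 11 |
| Power, log-normal, proportional (%) | 84 | 75 | 61 | 34 | 16 |
| Power, log-normal, additive (%) | 94 | 91 | 85 | 70 | 55 |

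Against the signed-rank test, the power difference at correlations 0.3 to 0.5 runs from a 12-point gain (log-normal, additive) to a 28-point loss (counts). At 0.7 it is a loss of 7 to 53 points, and at 0.8 of 23 to 67 points.

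**6. The same comparison with the effect held fixed.** Holding signed-rank power constant makes the effect smaller as correlation rises. With log-normal data and a fixed shift of 0.5 SD on the log scale:

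| Assumed correlation | 0 | 0.3 | 0.5 | 0.7 | 0.8 |
|---|---|---|---|---|---|
| Mann-Whitney power (%) | 32 | 30 | 26 | 25 | 22 |
| Signed-rank power (%) | 29 | 37 | 47 | 68 | 84 |

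Mann-Whitney power falls slowly, while the signed-rank test gains from the pairing.

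**The case against.** The strongest reply is that this is a naming slip. The very next sentence calls for paired tests and the design makes each patient his own control, so a reader would infer that the signed-rank test was meant. That is plausible, and it keeps the point from being graded higher. It does not rescue the text: a pre-specified plan should name a test that can be run, so that the choice is not left until the data are seen.

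Three further objections limit the size of the point. The reach is limited: the primary outcome as worded and the 50% reduction are responder outcomes. However, the SAP names tests only for continuous variables, so quality-of-life scores may in practice be tested this way. Next, the error is conservative, so under positive correlation a significant Mann-Whitney result would remain credible. Finally, the power figures rest on assumptions, and the 78% benchmark is not the trial's own, since its 80% refers to proportions. All three stand.

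It can also be said that the signed-rank test drops zero differences. In the count model these were 11 to 16% of pairs at correlations 0 to 0.5 and 19 to 21% at 0.7 to 0.8, with type I error at 4.7 to 5.0%. For an assumed five-level item, such as a Wexner component might be, zeros reached 25 to 52% under no effect, and type I error was still about 4 to 5%. This does not count against the change.

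**Conclusion.** The concern holds. For non-normal continuous variables the SAP names an independent-samples test and, in the next sentence, forbids it. This is an error as written, not merely missing detail, and it should be fixed.

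If Mann-Whitney were run, its true error rate would be about 2.1 to 2.4% at correlation 0.3, 0.7 to 0.9% at 0.5 and 0.1 to 0.2% at 0.7, instead of 5%. These rates are similar across the four data models, so they are the firmest part of the estimate. The power cost is less certain: at correlations up to 0.5 it depends on the distribution and can even be a gain, while at 0.7 and above all four models show a loss. Everything in the size estimate rests on assumed correlations and distributions; the contradiction itself rests on none. False-positive risk is not increased under positive correlation, and the stated sample size is untouched.

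**What to change.** In the sentence of the SAP that names the tests, replace the Mann-Whitney U test with the Wilcoxon signed-rank test, replace t-test with paired t-test, and state that normality is judged on the within-patient differences. The paired t-test wording only makes explicit what the next sentence already requires; the normality clause matters because the differences are what a paired test analyses.

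The cost is one sentence, with no change to design, data collection or sample size. The change removes the contradiction but does not settle which assessments are compared: Study design calls the first week baseline and the second control, scores are collected on five days, and the SAP does not say which are paired. That is a separate matter, which could be clarified in the same edit.

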### **Outcome variables:**

Primary outcomes:

- Any improvement in any of the domain explored by the Fecal Incontinence quality of life questionnaire[14].

Secondary outcomes:

-

- A 50% reduction in the number of episodes of FI or days per week, evaluated with the bowel diary and the weekly Wexner questionnaire.
- Any improvement in Wexner score, both total score and any of its components.
- Any improvement in quality of life score, and in any of its component.
- Usability score
- General satisfaction using a VAS score.
- Willingness of the patient to continue using the anal tape after the study.

Safety outcome:

- Any adverse effect that can be related to the device.

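### The any-domain primary outcome, tested at an unadjusted 5% per variable, raises the chance of a false improvement above the nominal 2.5% if domains are tested separately (about 6-10% assuming four domains)

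*Combined protocol and SAP*

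**What the plan says.** - Outcome variables, primary: "Any improvement in any of the domain explored by the Fecal Incontinence quality of life questionnaire". No domain is singled out, and no overall score, threshold or time point is given.
- Outcome variables, secondary: "Any improvement in quality of life score, and in any of its component". The same domains therefore appear in both lists.
- Statistical Analysis Plan: "Differences between the continuous variables during the control and the intervention period will be analyzed by t-test or the Mann-Whitney U test", depending on normality, and "Paired, Two-tailed tests with a significance level of 5% will be used in all analyses". There is no multiplicity adjustment or testing order, and no test for a binary outcome.
- Number of patients: "In this study each patient will be his own control before and after the intervention". The size is justified by "20 patients in each group are required to have a 80% chance of detecting, (with a significant 5% level" and by "an increase in 5 points in the quality of life questionnaire from 20% in the control period to 60% in the treatment period". That is one comparison of two percentages at one 5% level.
- Study procedures: quality of life is completed on days 0, 7, 14, 21 and 28. No section says which of these days enter the primary comparison.

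**The concern.** Read together, the outcome definition and the SAP describe a family of domain tests, each at 5%, in which one significant improvement is enough for primary success. The stated level then holds for each test but not for the primary claim. Listing the domains again as secondary outcomes means that the split between primary and secondary does not limit the family. The unnamed time points leave a further choice open.

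At stake is what a positive result would mean. In an open-label, non-randomized study of about 20 patients, the significance level is one of the few formal safeguards against a chance finding.

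**Working it through.** **The plan's own figure.** The 20 patients follow from the unpooled normal formula for two independent proportions, two-sided 5%, 80% power:

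n = (1.960 + 0.842)² × (0.2×0.8 + 0.6×0.4) / (0.6 − 0.2)² = 19.6, rounded up to 20.

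The study was therefore sized for one binary comparison, with no allowance for several domain tests.

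**Inputs for the error rate.**
- From the documents: n = 20, paired tests, two-sided 5% per test, success if any domain improves.
- Assumed: k, the number of domains (2 to 4 shown), and a common correlation between the domain change scores (0 to 0.8 shown).

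**Independent domains.** Only improvement can meet the primary outcome, and a two-sided 5% test gives a false improvement 2.5% of the time.
- False improvement in at least one domain: 1 − 0.975^k = 4.9% (k = 2), 7.3% (k = 3), 9.6% (k = 4).
- Significance in either direction: 1 − 0.95^k = 9.8%, 14.3%, 18.5%.

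**Correlated domains.** Simulated paired t-tests, n = 20, no true effect, equal correlation, at least 100,000 runs per setting:

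| Domains | Correlation | False improvement (nominal 2.5%) | Either direction (nominal 5%) |
|---|---|---|---|
| 2 | 0 | 4.9% | 9.8% |
| 2 | 0.8 | 3.9% | 7.8% |
| 3 | 0 | 7.4% | 14.3% |
| 3 | 0.8 | 5.0% | 10.0% |
| 4 | 0 | 9.6% | 18.6% |
| 4 | 0.5 | 8.0% | 15.9% |
| 4 | 0.8 | 5.8% | 11.5% |

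With four domains, the false-improvement rate is thus 5.8/2.5 = 2.3 to 9.6/2.5 = 3.8 times nominal.

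**Time points.** If days 21 and 28 were both tested for four domains (8 tests, same correlation throughout), the either-direction rate would be about 16% at correlation 0.8 and 34% at 0. The documents do not say that both days will be tested. The figure shows only why the day must be named.

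**A single test.** If the primary analysis is one comparison, whether of one score or of one yes/no responder variable, k = 1 and the rate stays at 5% (2.5% for improvement).

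**The case against.** The strongest reply is that the primary outcome may be one patient-level variable: the patient did or did not improve in any domain. The Number of patients section supports this, since it sizes the study on 20% versus 60% and the two-proportion formula reproduces its n. The Study design section also separates a baseline week from a control week, which would allow improvement to be judged in the control period too. One comparison of such a variable carries no domain multiplicity.

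This stands as a possible reading, and the documents do not exclude it. It does not remove the point. The SAP names tests for continuous variables only, and the 5-point increase in the sample-size section is not the same criterion as any improvement in any domain. On that reading the plan still lacks a definite responder rule and a test for it.

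A reader might also infer that the primary result has an error rate of 12-19% outright, up to almost four times the stated 5%. The documents do not support that. The range needs four domains and correlations between 0 and about 0.8, none of which is given. It also counts significant worsening, which cannot meet the primary outcome.

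Finally, the study is short, open-label and described as exploring efficacy. That bears on how serious the defect is, not on whether it exists.

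**Conclusion.** The defect holds, conditionally. If domains are tested separately, as the only written analysis implies, the nominal level does not apply to the primary claim. The chance of a false improvement is about 6-10% against 2.5% with four domains, and about 4-5% with two. The corresponding either-direction rates are about 12-19% and 8-10% against 5%.

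These ranges rest on assumed domain counts, an assumed common correlation from 0.8 down to 0, normally distributed differences and n = 20. The direction of the error needs only that there is more than one domain and that they are not perfectly correlated. The inflation disappears if one responder comparison is the sole primary test, but the plan would have to say so. This should be fixed; the conditional size and the exploratory setting do not justify a higher grade.

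**What to change.** 1. In Outcome variables and in the SAP, name one primary quality-of-life variable (for example one overall score), one control-period day and one treatment-period day (for example day 14 versus day 28). Test it once at two-sided 5%.
2. Restate the sample-size basis for that variable. For a continuous score this needs an assumed mean change and SD, which the documents do not give. For orientation, 20 pairs give 80% power at 5% for a change of 0.66 SD.
3. If one responder comparison was intended, say so, use the same responder rule in both sections and name a paired binary test such as McNemar's. For 20% versus 60%, the normal-approximation McNemar formula gives 17.1 to 26.9 patients as the share of patients who respond only in the control period goes from 0 to 0.10.
4. If the domains stay primary, apply Holm across them and claim only those that pass. With four domains the first step is 0.05/4 = 1.25%. For one given domain with a 0.66 SD effect (assumed) and n = 20, power at that step is about 58% instead of 80%. The loss is smaller for a claim on any domain: if all four shared that effect, the chance that at least one passes would be about 77% at correlation 0.8 and 97% at 0.
5. Remove the repeated domain item from the secondary list and label all other p-values as descriptive.

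The cost is revised outcome and SAP wording plus a restated sample-size justification. A single named variable carries no multiplicity penalty, but whether 20 patients suffice for it depends on the restated assumptions.
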